Title: POM-HR (Post Operative Morbidity- heart rate): Observational study of exercise-induced heart rate dynamics and their relationship to postoperative morbidity.

Short title: POM-HR

Objectives: Primary objective: To assess whether abnormal heart rate dynamics following cardiopulmonary exercise testing is related to postoperative complications and length of hospital stay.

Secondary objective: To assess whether abnormal heart rate dynamics following cardiopulmonary exercise testing is related to immune-inflammatory phenotypes and structural heart differences.

Type of trial: Unblinded, two-site, observational retrospective and prospective studies in elective surgical patients undergoing cardiopulmonary exercise testing (CPET) as part of their routine preoperative workup.

Trial design and methods: Retrospective study: Anonymized data detailing cardiopulmonary exercise tests and postoperative morbidity/ length of stay that are collected and assessed routinely as part of clinical care will be provided by both centres.

Prospective study: Preoperative patients undergoing major surgery are referred routinely for

cardiopulmonary. All heart rate data is derived from cardiopulmonary exercise testing acquired data, performed as part of their routine preoperative workup.

Blood derived immune cells will be acquired at UCLH site only pre and post exercise from from indwelling catheters routinely placed for the CPET itself.

Transthoracic (non-invasive) echocardiography will be performed pre and post CPET at the UCLH site only.

Postoperative morbidity and complications will be recorded on days 3, 5, 7, 10 and 14 if the patient remains in hospital for that length of time. This is routinely collected in both hospitals.

Trial duration per participant: 6 weeks, including duration between consent CPET and end of surgical hospital stay.

[figure not shown]
Estimated total trial duration: 4 years

Planned trial sites: University College London Hospital;
Derriford Hospital, Plymouth

Total number of participants planned: 1356

Main inclusion criteria: All surgical patients referred for cardiopulmonary exercise testing preoperatively by their surgical or anaesthetic consultant undergoing major noncardiac surgery.

5. Flowchart of events:

6. Background

Hypothesis

To demonstrate that autonomic dysfunction (as reflected by heart rate response to exercise) is predictive of short-term postoperative morbidity and length of stay.

Background

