For the retrospective study, pre-existing nonidentifiable morbidity and preoperative cardiopulmonary exercise test data is acquired as part of the clinical quality monitoring at both hospitals and can be provided by the clinical care teams thus ensuring no breach of confidentiality. These data are fully anonymised and do not include any potential identifiers.

For the prospective study: All heart rate data is derived from cardiopulmonary exercise testing acquired data, performed as part of their routine preoperative workup. Blood derived immune cells will be acquired at UCLH site only pre and post exercise from from indwelling catheters routinely placed for the CPET itself. Ex-vivo laboratory studies will explore bioenergetic (mitochondrial) function in leukocyte subsets and Immune function in leukocyte subsets. Transthoracic (non-invasive) echocardiography will be performed pre and post CPET at the UCLH site only. Postoperative morbidity and complications will be recorded on days 3, 5, 7, and 14 if the patient remains in hospital for that length of time. This is standard practice in both hospitals.

UCLH has a strong record of perioperative research in this area. As such our local patients are fully engaged in the perioperative research process. Our Critical Care patient liaison group is a strong advocate of patient centred outcomes research. We also have patient representatives via the Centre for Anaesthesia Patients Information Group, who participate in our monthly clinical research meetings to present patient views on research, protocols and enrolment issues (<http://www.ucl.ac.uk/anaesthesia/patients>).

9. Selection of subjects and Informed consent procedure

Recruitment

Patient recruitment will only be done when the trial has

1. Documented REC, Regulatory and Local Trust R&D approval
2. A signed site agreement
3. The site has sent back to the TC the PI self-monitoring template.

10. Subject selection

Inclusion criteria

All surgical patients referred for cardiopulmonary exercise testing preoperatively by their primary surgeon or anesthesiologist undergoing major noncardiac surgery.

Exclusion criteria

1. history of exercise induced angioedema,
2. pregnancy,
3. any contraindication to cardiopulmonary exercise testing (as outlined by American Association of Anaesthesia):

Consent procedure

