For the retrospective study, we have written confirmation from the NIGB ([name], Ethics and Confidentiality Committee; [contact]) that nonidentifiable morbidity and preoperative cardiopulmonary exercise test data can be provided by the clinical care teams thus ensuring no breach of confidentiality. Pre-existing nonidentifiable morbidity and preoperative cardiopulmonary exercise test data is acquired as part of the clinical quality monitoring at both hospitals and can be provided by the clinical care teams ensuring no breach of confidentiality. These data are fully anonymised and do not include any potential identifiers. It is the responsibility of the principal investigator and co-investigator to ensure written informed consent from each subject prior to participation in this study. Responsibility for conducting the informed consent process may be delegated to appropriately trained members of the research team (see 18. definition of responsibilities). This process will include an explanation of the aims, methods, anticipated benefits and potential hazards of the study. The CPET service will highlight potential patients ahead of their attendance at surgical clinic, several weeks before the initiation of the study. No healthcare professionals involved in the patients perioperative care will be involved in the consent process. The principal investigator and co-investigator will explain to all potential participants that they are free to refuse to enter the study or to withdraw at any time during the study, for any reason. The patients will be approached prior to the CPET, thereby affording suitable time for patients to consider the process of consent. The principal investigator and co-investigator

will be contactable by mobile phone and electronic mail to address further queries. Where a patient wishes to be withdrawn from the study, only the primary outcome data will be collected to enable intention treat analysis. Non-English speakers will be provided with full access to NHS translation services to ensure appropriate understanding of the trial and consent process. We will not recruit patients who lack capacity to give or withhold informed consent. A copy of the signed Informed Consent will be given to the participant. The original signed form will be retained at the study site.

11. Risks, burdens and benefits

Risks and burdens

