There are no study specific risks introduced by this study since we are utilizing preoperative data from routine investigations and postoperative outcomes. CPET preoperative investigation represent routine care at UCLH and Derriford hospitals. Post Operative Morbidity Survey data is routinely collected at UCLH and Derriford, so represent standard of care at our institutions.

Benefits

1. The information we get from this study may help us to better treat future patients undergoing surgery and those who are seriously ill in intensive care.

12. Randomisation

Observational study- not applicable.

13. Definition of end of trial

The end of the trial will be the date of the last visit by the last participant.

14. Conflicts of Interest

There are no conflicts of interests for this study. After the study has ended, the results will be fed back to all participants and patient representatives via the Centre for Anaesthesia Patients Information Group, which we invite to participate in our monthly meetings.

Use of tissue samples in future research

Samples will be stored securely within Wolfson Institute for Biomedical Research, UCL. These samples will be used to investigate cellular processes that may be involved in perioperative complications. The CI is the only investigator authorized to use these samples. All subsequent amendments will be notified.

15. Data management and quality assurance

Confidentiality/data handling and analysis

For the retrospective study, we have written confirmation from the NIGB ([name], Ethics and Confidentiality Committee; [contact]) that nonidentifiable morbidity and preoperative cardiopulmonary exercise test data can be provided by the clinical care teams thus ensuring no breach of confidentiality. These data are fully anonymised and do not include any potential identifiers. Submitted data will be coded (pseudoanonymised) and reviewed for completeness and consistency and then entered on a database. To ensure validity and quality, double data entry will be performed.

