Data will be entered from paper CRFs onto access database by responsible investigator(s) at the Derriford study site. Participants will be identified by study number only so that confidentiality will be maintained. The access database will be sent by secure nhs email from the Principal Investigator at Derriford to the Chief Investigator at UCL. Thus no patient identifiable data will leave the Derriford site.

Record Keeping and archiving

Chief Investigators are responsible for the secure archiving of trial documents and the trial database.

16. Statistical analysis

Statistician involved in powering the study: [name], Department of Health Services Research and Policy, Institution London School of Hygiene + Tropical Medicine
[name]. [contact]

Surgical Patients – Sample size

Primary outcome is incidence of morbidity on postoperative day 5. 40% of patients undergoing major surgical procedures sustain defined morbidity on postoperative day 5. From the cardiovascular literature, the relative risk of predicted morbidity is $\geq 2x$ more prevalent in patients with abnormal heart rate recovery (HRR), who we predict may constitute up to 50% of the patient population. If 50% abnormal HRR patients sustain postoperative morbidity compared with 30% patients exhibiting normal HRR preoperatively, with power =80%, 339 patients per group would be required to detect this difference in postoperative morbidity ($\alpha=0.05$). Since two sites are collecting data to demonstrate that this is not a site-specific phenomenon, the total number of patients is therefore 1356 (retrospective and prospective studies).

Surgical Patients – Statistical analysis

The primary analysis is to examine the relationship between exercise-induced abnormal HRR and the development of postoperative morbidity. The chi-square test will be used for an initial comparison, and subsequently logistic regression will be used to examine HRR and additionally the effects of preoperative factors upon postoperative morbidity. The log rank test and Cox regression will be used for equivalent analyses for the length of stay in hospital. The unpaired t-test or Mann-Whitney test will be used to compare cellular and heart rate variables between patients with normal/ abnormal HRR.

Direct access to source data/documents

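### The withdrawal rule serves an intention-to-treat analysis that this observational study cannot have, and it stops later collection of length of stay and, before the exercise test, of the exposure

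*Protocol*

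**What the plan says.** The rule is one sentence in the protocol's consent procedure (section 10). For a patient who asks to withdraw, "only the primary outcome data will be collected to enable intention treat analysis". The same section has patients approached before CPET and lets them leave at any time.

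Other parts of the protocol bear on it:

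- Section 12 (Randomisation): "Observational study- not applicable".
- Synopsis, type of trial: "Unblinded, two-site, observational retrospective and prospective studies in elective surgical patients".
- Section 16, sample size: "Primary outcome is incidence of morbidity on postoperative day 5".
- Synopsis, primary objective: whether abnormal heart rate dynamics "is related to postoperative complications and length of hospital stay".
- Section 8, source of the exposure in the prospective study: "All heart rate data is derived from cardiopulmonary exercise testing acquired data, performed as part of their routine preoperative workup".

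Section 16 plans a chi-square test and then logistic regression with preoperative factors for morbidity by HRR. It plans log rank and Cox analyses for length of stay.

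**The concern.** In a randomised trial, a rule of this kind works because the comparison group is known from the moment of allocation, so the primary outcome is the only item still needed. Here the comparison group is itself a measurement made at CPET. The outcome alone is therefore not always enough, and the stated reason for collecting it after withdrawal does not apply. The sentence reads as carried over from a randomised template. Section 15 likewise keeps instructions for breaking a treatment code, in a study with no treatment allocation.

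The word *only* makes this a restriction on collection, not a detail left open. An analysis plan cannot recover data that the protocol told sites not to collect. At stake is an endpoint named in the primary objective, which could be lost selectively if, for example, patients with a difficult or prolonged stay are more likely to withdraw.

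**Working it through.** **1. What each planned analysis needs, and what the rule leaves.** The rule is read as limiting collection after withdrawal, with data already recorded kept.

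| Time of withdrawal | HRR class | Preoperative factors | Day-5 morbidity | Length of stay |
|---|---|---|---|---|
| Before CPET | not collected | only if already recorded | collected | not collected |
| After CPET, before surgery | already recorded | normally recorded | collected | not collected |
| After surgery, before discharge | already recorded | recorded | collected | incomplete |
| After discharge | already recorded | recorded | already recorded or collected | already recorded |

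Consequences for the analyses in section 16:

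- Chi-square test (needs HRR and day-5 morbidity): impossible in the first row, possible in the other three.
- Logistic regression (also needs preoperative factors): impossible in the first row, possible in the others where the factors were recorded.
- Log rank and Cox (need HRR and length of stay): no contribution from the first two rows. The third row can contribute only as censored at withdrawal. The fourth is unaffected.

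**2. Who can be affected.** Only consented prospective patients can withdraw, because the retrospective data are anonymised. The protocol gives one total, 1356, for both parts and does not state the prospective number or an expected withdrawal rate. The number affected cannot be calculated.

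**3. Is power at risk?** The inputs from section 16 are morbidity of 50% against 30%, α = 0.05 (two-sided assumed, as sidedness is not stated), equal groups, and 339 per group at each of two sites. The total is 339 × 2 × 2 = 1356, as stated.

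The formula for the number per group is n = [z(α/2)·√(2p̄q̄) + z(β)·√(p₁q₁ + p₂q₂)]² / (p₁ − p₂)², with p̄ = 0.40.

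- First term: 1.96 × √0.48 = 1.358.
- Second term at 80% power: 0.842 × √0.46 = 0.571.
- n = (1.358 + 0.571)² / 0.04 ≈ 93 per group, or 103 with continuity correction.

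The stated 339 is not reproduced. That is a separate matter and does not bear on the withdrawal rule, except that it leaves a wide margin.

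Power at a given n is Φ[(0.20·√n − 1.358) / 0.678]. The loss rates below are assumptions.

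| Assumed share not analysable | n per group per site | Power |
|---|---|---|
| 0% | 339 | 99.97% |
| 1% | 336 | 99.97% |
| 5% | 322 | 99.95% |
| 10% | 305 | 99.92% |
| 20% | 271 | 99.78% |

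The table applies the loss to the whole of a site's sample, so it overstates the effect where part of that sample is retrospective. Under the protocol's own rates, power is not the problem.

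**The case against.** The strongest reply is that the rule does most of its job. It limits what is collected from withdrawal onward, and nothing in the protocol says that earlier records are discarded. HRR comes from a single preoperative test and the covariates predate surgery. For anyone who withdraws after CPET, the one item still outstanding for the primary comparison is day-5 morbidity, which the rule secures. This stands. A reader might infer that withdrawn patients in general cannot be analysed, or that their outcomes have no analytic use. The documents do not support either inference.

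It can also be said that a patient who leaves before CPET has not yet been classified, so the loss resembles non-participation more than differential loss from an HRR group. That is fair and limits the bias from this source. The rule would still collect an outcome from such a patient with no use in the stated comparison.

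On length of stay, log rank and Cox methods can censor a patient who withdraws in hospital. They do so without bias only if withdrawal is unrelated to remaining stay given the model, and the protocol gives no ground for assuming that. Patients who withdraw before surgery contribute nothing. A site might read primary outcome broadly enough to include length of stay, because the primary objective does, but section 16 defines it as day-5 morbidity.

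Finally, the consent form and information sheet are not available here and may offer withdrawal options. If so, they would need to agree with the protocol sentence, which as it stands is restrictive.

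**Conclusion.** The point holds in a limited form. The rule rests on an analysis that cannot exist in this design. It stops collection of length of stay for prospective patients who withdraw before discharge, and of HRR for those who withdraw before CPET. After CPET, the day-5 analyses remain open to withdrawn patients.

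The size is unknown and probably small. A reader might apply an assumed withdrawal rate to the planned total: 2% to 5% of 1356 is 27 to 68. Those figures are not supported. The rate is assumed, the denominator includes retrospective patients who cannot withdraw, and the count would mix all withdrawals with the few that precede CPET. Nor do the documents support a claim of lost power. What remains is possible selective loss, mainly from the length-of-stay analysis, and post-withdrawal collection justified on a ground that does not apply.

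This rests on reading the sentence as a limit on later collection and on section 16's definition of the primary outcome. The change is still worth making, because the data at issue are largely held as routine care.

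**What to change.** Replace the sentence in the consent procedure with a rule that:

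- drops the reference to intention to treat and states that patients are analysed in their measured HRR group;
- states that data recorded before withdrawal are kept;
- for a patient who withdraws from the research procedures (blood sampling, echocardiography) but agrees to continued use of routine data, provides for collection of routine CPET heart-rate data, preoperative factors, morbidity and length of stay;
- for a patient who refuses all further data use, collects nothing more.

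A patient who withdraws before CPET and agrees to routine data use then has an HRR class if the routine test goes ahead. If no HRR is ever recorded, the rule should say that the patient is not in the HRR comparison.

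The cost is one protocol paragraph and an option on the withdrawal form, with matching text in the information sheet if needed. Section 17 requires ethical and regulatory approval if the amendment counts as substantial. Patients who refuse all data use will no longer supply day-5 morbidity, which the present rule would have collected. That loss should be reported as a count by time of withdrawal.

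### The 339 patients per group in Section 16 do not follow from the inputs given (50% vs 30%, 80% power, alpha 0.05), which need about 93; the study is larger than its stated basis requires

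*Protocol*

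**What the plan says.** All the inputs stand in the sample size paragraph of Section 16 (Statistical analysis).

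- Endpoint: "Primary outcome is incidence of morbidity on postoperative day 5".
- Overall rate: "40% of patients undergoing major surgical procedures sustain defined morbidity on postoperative day 5".
- Share with abnormal HRR: "who we predict may constitute up to 50% of the patient population".
- Rates by group: "If 50% abnormal HRR patients sustain postoperative morbidity compared with 30% patients exhibiting normal HRR preoperatively".
- Result: "with power =80%, 339 patients per group would be required to detect this difference in postoperative morbidity", with alpha given as 0.05 and no statement of one or two sides.
- Total: because two sites are to show that the finding is not specific to one of them, "the total number of patients is therefore 1356 (retrospective and prospective studies").

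The synopsis repeats the total: "Total number of participants planned: 1356". The analysis paragraph of Section 16 names a chi-square test first, followed by logistic regression. The sample size paragraph gives no allowance for dropout, covariates, clustering, multiplicity or a comparison between sites.

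**The concern.** A 20-point difference around a 40% rate is large, and a requirement of 339 per group for only 80% power looks several times too high. The paragraph ties 339 to the stated rates, power and alpha and to nothing else, so the sentence can be checked directly.

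If it fails, at least one of the rates, the power or the number is misstated. A reader then cannot tell whether the study was sized for a 20-point difference or for something much smaller, and cannot judge the eventual result, positive or null, against the design. The planned total rests on the same figure.

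**Working it through.** **Inputs (all from Section 16).** p1 = 0.50, p2 = 0.30, difference 0.20, mean 0.40, power 80%, alpha 0.05. Two assumptions are mine: a two-sided test (z = 1.960, with 0.842 for 80% power) and equal groups, the latter matching the 50% share.

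The design inputs agree with each other: 0.5 x 50% + 0.5 x 30% = 40%, the stated overall rate.

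**Step 1. The total.** 339 x 2 groups x 2 sites = 1356. This reproduces.

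**Step 2. The number per group.** With pooled variance under the null hypothesis,

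n = [1.960 x sqrt(2 x 0.40 x 0.60) + 0.842 x sqrt(0.50 x 0.50 + 0.30 x 0.70)]² / 0.20²

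= (1.358 + 0.571)² / 0.04 = 93.0 per group.

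With continuity correction, n' = (n/4) x [1 + sqrt(1 + 4/(n x 0.20))]² = 102.8, so 103. The figure of 339 does not reproduce.

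**Step 3. Other readings of the same inputs.**

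| Variant (50% vs 30%) | Per group | With continuity correction |
|---|---|---|
| Two-sided, 80% power | 93 | 103 |
| Two-sided, unpooled variance | 91 | – |
| Two-sided, arcsine | 93 | – |
| One-sided, 80% power | 74 | 83 |
| Two-sided, 90% power | 124 | 134 |
| Two-sided, 99.9% power | 299 | 309 |

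None reaches 339. Unequal groups do not explain it either. At a 20% share with abnormal HRR, the requirement is 285 patients for a whole site (315 with continuity correction), against 678 planned per site. Reading 339 as one site's total contradicts the wording and still gives 96.7% power with about 170 per group.

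**Step 4. Power at 339 per group.**

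- Standard error under the null: sqrt(0.40 x 0.60 x 2/339) = 0.0376.
- Standard error under the alternative: sqrt((0.25 + 0.21)/339) = 0.0368.
- z = (0.20 – 1.960 x 0.0376) / 0.0368 = 3.43, so power = 99.97%.

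**Step 5. What 339 per group detects with 80% power.** Solving the Step 2 formula for a difference centred on 40% gives about 10.5 points (about 45.3% vs 34.7%), or 10.8 points with continuity correction. That is about half the stated difference.

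**Step 6. Sensitivity to the share with abnormal HRR.** The protocol gives 50% only as an upper figure. At a 20% share, a site of 678 has about 136 and 542 patients, and power for 50% vs 30% is about 99%. Holding those rates fixed at that share implies an overall rate of 0.2 x 50% + 0.8 x 30% = 34%, not 40%. For the 10.5-point difference, per-site power at a 20% share falls to about 61–62%, so the 80% in Step 5 holds for equal groups only.

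**The case against.** The best defence is that the error is on the safe side. The study has more power than claimed for its stated effect, and this survives a much smaller share with abnormal HRR. Type I error and the choice of primary test are untouched. The study is observational, exercise testing and morbidity recording are routine care at both hospitals, and part of the 1356 is existing anonymised data. All of this stands. It limits the weight of the point but does not make the sentence correct.

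The number might also contain an unstated allowance for dropout, adjustment or a comparison between sites. But the paragraph attributes 339 to the rates, power and alpha alone, and the doubling for sites comes afterwards. A statistical analysis plan could add detail but could not make this sentence true.

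A reader might infer more than the protocol supports:

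- *That the twofold risk from the cardiovascular literature contradicts 50% vs 30% (a relative risk of 1.67).* It does not. The literature figure is background, and planning on a smaller effect is ordinary caution.
- *That too many prospective patients are asked to consent.* The protocol gives no prospective number; 1356 covers both studies, so no excess can be worked out.
- *That clinically small differences will come out significant.* Nothing in the protocol supports calling about 10.5 points clinically small.
- *That 1356 is a second error.* The multiplication is right; only the 339 in it is at fault.

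**Conclusion.** The point holds as an arithmetic error in a stated design figure. The stated inputs require about 93 per group (103 with continuity correction), so 339 is about 3.6 (3.3) times too many, and the power at 339 is 99.97% instead of 80%. This assumes a two-sided test and equal groups; a one-sided test widens the gap, and unequal groups do not close it.

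The study is over-powered, not under-powered, for 50% vs 30%, and its validity is not harmed. What is wrong is the stated power and required number, and with them the reader's ability to see what effect the study is sized for. The protocol does not show whether the rates, the power or the number was misstated, and nothing in it says that 10.5 points was ever the intended target. This should be corrected, but it is no obstacle to the conduct of the study.

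**What to change.** The sponsor should reconcile the rates, power and number in the sample size paragraph of Section 16, by one of two routes.

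1. **Keep 1356 and state what it delivers (cheapest).** With equal groups, 339 per group per site gives over 99.9% power per site for 50% vs 30%, and 80% power per site for a difference of about 10.5 points around the stated 40% rate. The second figure should be described as what the size can detect, unless the sponsor can show that it was the design target. This costs a few sentences in Section 16; the synopsis and enrolment stay as they are.
2. **If 50% vs 30% at 80% power was the intended basis, state 93 per group (103 with continuity correction).** With the protocol's own multiplication the total becomes 93 x 4 = 372 (103 x 4 = 412). The synopsis would then change too, and so would the planned enrolment.

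Under route 1, state whether alpha is one- or two-sided. Because 50% is only an upper figure for the share with abnormal HRR, add that per-site power for 50% vs 30% with 678 patients is still about 99% at a 20% share, and that the 10.5-point figure assumes equal groups.

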Complications following surgery are an important cause of morbidity and mortality. When these complications occur within 30 days of major surgery a patients' long term survival may be compromised [1]

Heart rate recovery is an independent predictor of longer term cardiovascular disease outcomes. Beyond the heart, the vagus nerve plays important roles in reducing inflammation and protecting cells from various stresses. The rate of heart rate recovery following exercise reflects how well the vagus nerve works. Standardized exercise tests allow us to measure how well the vagus nerve is working, and therefore provide important insights into whether the vagus nerve helps protect cardiac function and noncardiac effects in different patients undergoing major surgery. POM-HR is a mechanistic study designed to examine if abnormal heart rate recovery can identify patients who are at greater risk of complications post-operatively through abnormal autonomic activation. Studies have suggested that the central nervous system controls the body's response to inflammation. The vagal nerve is an important nerve in the central nervous system and has an influence on organs such as the spleen and liver which help dampen down inflammation. Experimental model studies have shown that signals via the vagal nerve can inhibit inflammation and improve outcomes in various disease processes including models of sepsis, myocardial ischaemia and ileus.[5-13] Understanding this mechanism in a clinical context may help us to understand why some patients sustain complications after surgery. This will allow future clinical care to be guided by an understanding of why these complications arise and allow early detection, treatment and avoidance of postoperative morbidity.

7. Purpose

There is a need to confirm that a vagal neuro-immune activation is linked to postoperative complications. Demonstrating that a vagally controlled neuro-immune activation is linked to reduced postoperative complications in surgical patients will enhance our understanding of the underlying

mechanisms. This investigation could then encourage a widespread use of simple interventions, such as preoperative exercise regimes, to enhance vagal activation following all types of surgery to reduce morbidity postoperatively.

8. Study design

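### For post-exercise immune values, the named unpaired tests cannot separate HRR group from exercise dose if work done on the CPET differs between the groups (low severity)

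*Protocol*

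**What the plan says.** The secondary objective in the synopsis is "To assess whether abnormal heart rate dynamics following cardiopulmonary exercise testing is related to immune-inflammatory phenotypes and structural heart differences". For the immune part, section 8 (Study design) states: "Blood derived immune cells will be acquired at UCLH site only pre and post exercise". The exercise is the clinical CPET, "performed as part of their routine preoperative workup", and not a test designed for the study. The protocol gives no workload, ramp, stopping criterion or time for the post-exercise sample.

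Section 16 (Statistical analysis) names the analysis: an unpaired t-test or Mann-Whitney test "will be used to compare cellular and heart rate variables between patients with normal/ abnormal HRR". It does not say whether resting values, post-exercise values or changes are compared, and it names no covariate. The same paragraph goes beyond the unadjusted test for the clinical outcomes. For morbidity, after the chi-square test, "subsequently logistic regression will be used to examine HRR and additionally the effects of preoperative factors upon postoperative morbidity". Length of stay gets Cox regression after the log rank test. Cellular variables get only the two-group test.

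**The concern.** Exercise is the stimulus applied between the two blood samples, and HRR is measured on the same test. If patients with abnormal HRR do a different amount of work, and if the amount of work affects leukocyte numbers or function, then the post-exercise values of the two groups differ for a reason other than vagal function. An unpaired test assigns that whole difference to HRR group. Subtracting the pre-exercise value does not help, because it removes differences present at rest and leaves the unequal stimulus in place. A larger sample does not help either: the bias stays the same while the standard error shrinks, so a false positive becomes more likely.

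At stake is the interpretation of the post-exercise immune results. Sections 6 and 7 present the study as mechanistic and aim to link vagal neuro-immune activity to complications. A difference due to exercise dose could be read as evidence for that link.

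**Working it through.** **No stated figure to reproduce.** The protocol gives no sample size, power or effect size for the cellular comparison. Its 339 per group is for morbidity ("If 50% abnormal HRR patients sustain postoperative morbidity compared with 30% patients exhibiting normal HRR preoperatively") and is not used here.

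**What the protocol supplies.** Two HRR groups, expected to be roughly equal in size (up to 50% abnormal, section 16); sampling before and after exercise at UCLH only; an unadjusted two-group test at an assumed two-sided 5% level.

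**What has to be assumed.** None of the following is in the protocol:
- g: difference in mean work done between HRR groups, in within-group SDs (0.3 to 0.8).
- r: within-group correlation of work done with the post-exercise value or change (0.2 to 0.5).
- n: patients per HRR group in the UCLH immune subset (30 to 150).
- A linear relation between work and response, and no effect of HRR itself.

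**Step 1, spurious difference.** In SD units, d = r × g.

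**Step 2, rejection probability.** With n per group and within-group SD 1, the standard error is √(2/n). By the normal approximation,

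P(reject) = Φ(d√(n/2) − 1.96) + Φ(−d√(n/2) − 1.96).

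For example, g = 0.8 and r = 0.4 give d = 0.32. At n = 100, d√(n/2) = 0.32 × 7.07 = 2.26, so P(reject) ≈ Φ(0.30) ≈ 0.62, the second term being negligible.

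| Gap g (SD) | Correlation r | d | n per group | d√(n/2) | P(reject), no HRR effect |
|---|---|---|---|---|---|
| 0.3 | 0.2 | 0.06 | 30 | 0.23 | 5.6% |
| 0.3 | 0.2 | 0.06 | 100 | 0.42 | 7.1% |
| 0.5 | 0.3 | 0.15 | 30 | 0.58 | 8.9% |
| 0.5 | 0.3 | 0.15 | 100 | 1.06 | 18.6% |
| 0.8 | 0.4 | 0.32 | 50 | 1.60 | 36% |
| 0.8 | 0.4 | 0.32 | 100 | 2.26 | 62% |
| 0.8 | 0.4 | 0.32 | 150 | 2.77 | 79% |
| 0.8 | 0.5 | 0.40 | 30 | 1.55 | 34% |
| 0.8 | 0.5 | 0.40 | 100 | 2.83 | 81% |

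**Step 3, effect of adjustment.** In this linear model HRR group has no effect once work done is held fixed. Adding work performed as a covariate therefore returns the rejection rate to about 5%.

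**Step 4, resting samples.** These are drawn before the exercise, so the dose of this test cannot affect them. The table does not apply to them.

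**The case against.** The strongest reply is that the protocol does not establish the premises. It does not say that work differs by patient or by HRR group, that patients with abnormal HRR do less, or that the cellular measures depend on dose. This stands: the size and direction of any bias cannot be derived, and with a small gap and weak correlation the inflation is slight (5.6% to 7.1%). A reader might infer that an immune difference between HRR groups would be an artefact of exercise dose. The protocol does not support that reading; it shows only that the named tests could not rule it out.

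Section 6 does say "Standardized exercise tests allow us to measure how well the vagus nerve is working". That describes exercise tests in general. It fixes no common workload, so it does not answer the concern.

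The time point to be compared may be settled in a statistical analysis plan that is not at hand, and the resting sample may already be the intended comparison. That is possible and limits the scope. The choice of an unpaired test is nevertheless stated in the protocol, beside regression for the other outcomes, so it is more than a detail left open.

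The objective asks only whether HRR is related to immune phenotype, and an unadjusted comparison answers that as worded. It does not support the mechanistic interpretation for post-exercise values.

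Finally, work done may itself reflect vagal function or lie between it and the immune response, and HRR is measured after that same work. Adjustment could then remove part of the effect of interest. This also stands. It argues against making the work-adjusted model the only analysis, and for reporting it beside the model without work.

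**Conclusion.** The point holds conditionally. If work performed differs between HRR groups and influences the cellular response, the unpaired tests in section 16 cannot separate HRR from exercise dose for post-exercise values or pre-to-post changes. Under the assumed inputs, the false-positive rate of a nominal 5% test runs from about 6% to about 80%. Every input is an assumption, so this range is an illustration and not an estimate for this study.

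It would be tempting to say that the study's whole mechanistic case rests on this comparison. The protocol does not support that: resting samples and echocardiography also serve the secondary objective, and the primary objective is clinical. Severity is low, since this is a secondary objective with sampling at one site.

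**What to change.** In section 16, for cellular variables:

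1. Name the resting (pre-exercise) sample as the comparison of immune phenotype between HRR groups. The unpaired test can stay for this.
2. For post-exercise values, replace the unpaired test with a linear model containing HRR group and the pre-exercise value. This uses samples already collected. It does not by itself deal with exercise dose.
3. Report the same model with work performed on that CPET added (peak work rate or exercise time, assumed available from the CPET record). State that this estimate is conditional on work done and may remove part of a vagal effect if work lies on that pathway. Show both estimates together.

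The cost is a few lines of text and one covariate from a test already being done, with no added procedure for patients. The downsides are slightly wider intervals where HRR and work done are correlated, and the need to state the mediation caveat with the result.
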